16.1.1.3. Clinical Global Impressions Scale – Bipolar Version - Severity of Illness (CGI-BP-S)

The CGI-BP-S is a clinician-rated assessment of the subject's current illness state (mania, depression, and overall bipolar illness), measured at Screening, Baseline, Weeks 1 to Week 28 for subject outside Japan and Week 1 to Week 52 for subject within Japan.

A clinician assesses the subject's current illness on a 7-point scale ranging from 1= 'Normal, not ill' to 7= 'Very severely ill'. Higher scores are associated with greater illness severity.

16.1.1.4. Sheehan Disability Scale (SDS)

The SDS is a composite of 5 self-rated items designed to measure the extent to which 3 major sectors in the subject's life are impaired by depressive symptoms, measured at Screening, Baseline, Weeks 4, 12, 20 and 28 for subject outside Japan and Weeks 4, 12, 20, 28, 36, 44 and 52 for subject within Japan.

Three items are self-rated using a 10-point visual analog scale ranging from 0 to 10 to assess disability across three domains: work/school, social life, and family life. The three items will be summarized individually in addition to the SDS total score. The final two items ask patients about the number of days on which their symptoms caused them to miss school and/or work and the number of days on which their symptoms caused them to be underproductive at school and/or work (both items not included in the SDS total score).

The SDS total score is calculated as the sum of the 3 first items and ranges from 0 (Not at all) to 30 (Extremely). If one or more items are missing at a visit, as can occur when a subject opts out of the work/school item because it does not apply, the total score will be set to missing.

16.1.1.5. Hamilton Rating Scale for Anxiety (HAM-A)

The HAM-A is a 14-item rating scale developed to quantify the severity of anxiety symptomatology, measured at Screening, Baseline, Weeks 4, 12, 20 and 28 (for subject outside Japan) and Weeks 4, 12, 20, 28, 36, 44 and 52 for subject in Japan.

The 14 items are: anxious mood, tension, fears, insomnia, intellectual, depressed mood, somatic (muscular), somatic (sensory), cardiovascular symptoms, respiratory symptoms, gastrointestinal symptoms, genitourinary symptoms, autonomic symptoms, and behavior at interview. Each of the 14 items is rated on a 5-point scale, ranging from 0 (not present) to 4 (severe/disabling).

The HAM-A total score is the sum of the 14 individual items and ranges from 0 to 56. Higher scores are associated with a greater degree of anxiety. If one or more items are missing at a visit, the total score will be set to missing.

16.1.1.6. Time to recurrence/relapse of any mood event from clinical stability of bipolar disorder

Clinical stability is defined as a total score of ≤ 12 on the YMRS and the MADRS over at least 12 weeks, with the allowance of 2 excursions (the YMRS and/or MSDRS total scores up to 13 or 14, respectively) except during the last 4 weeks before achieving clinical stability.

Duration of stabilization period is defined as the time period during which subjects achieve and maintain

Document:	K:\DSP\SM-13496\RVA97109\Biostatistics\Documentation\SAP		
Author:	[REDACTED]	Version Number:	1.0
		Version Date:	20MAR2018

Template No: CS_TP_BS016 – Revision 3
Effective Date: 01May2012

Reference: CS_WI_BS005

Copyright © 2012 [REDACTED] All rights reserved.
The contents of this document are confidential and proprietary to [REDACTED]. Unauthorized use, disclosure or reproduction is strictly prohibited.

clinical stability during the study. If a subject experiences > 2 excursions within the projected stabilization period, the stabilization "clock" must be restarted and counting of weeks of the stabilization period will start again. The duration of the stabilization period will be calculated as: ((date of stabilization – date of first dose of study medication) +1).

Recurrence/relapse of any mood event is defined as any of the following criteria:

1. Fulfilled DSM-IV-TR criteria for major depressive, manic, mixed, hypomanic episode
2. Required treatment intervention for major depressive, manic, mixed or hypomanic episode symptoms with any antipsychotic (other than study medication), antidepressant, mood stabilizer (other than lithium or VPA), anxiolytic or benzodiazepine (beyond dosage allowed for anxiety, agitation or insomnia in the protocol)
3. Psychiatric hospitalization for any bipolar mood episode
4. YMRS or MADRS total score ≥ 18 or at least one of the CGI-BP-S (overall, depression, mania) scores ≥ 4 at two consecutive assessments no more than 10 days apart
5. Discontinuation from the study because of a mood episode (as determined by the Investigator)

Time to recurrence of any mood event from clinical stability is defined as ((date of first recurrence of any mood event – clinical stability date) + 1). Time to recurrence will be censored at the time of study completion or early termination, defined as ((date of study completion or discontinuation – clinical stability date) + 1), for subjects who discontinue or complete the study without experiencing any recurrence of mood event.

16.1.1.7. Time to All-cause Discontinuation

The time to all-cause discontinuation is defined as ((date of discontinuation – date of first dose of study medication) + 1). When a subject completes the study, the time to event is censored at the time of study completion.

16.1.2. SENSITIVITY ANALYSIS VARIABLES

16.1.2.1. Time to Recurrence of a Major Depressive, Manic, Mixed, Hypomanic Episode

Time to recurrence of a major depressive, manic, mixed or hypomanic episode is defined as ((date of first episode of any mood event – date of clinical stability) + 1). When a subject completes the study without experiencing any mood event, the time to event may be censored at the time of study completion or discontinuation.

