9.5.2 Efficacy analysis

Summary statistics in the following efficacy variables will be provided for all patients and by treatment group in the prior study. Note that summaries at visits after 28 weeks as well as at Week 52 (LOCF) will only be provided for patients enrolled in Japan.

- Change from DB and LT baselines in the MADRS total score at each scheduled assessment, Week 28 (LOCF) and Week 52 (LOCF)
- Change from DB and LT baselines in the YMRS total score at each scheduled assessment, Week 28 (LOCF) and Week 52 (LOCF)
- Change from DB and LT baselines in the CGI-BP-S score (overall, depression, mania) at each scheduled assessment, Week 28 (LOCF) and Week 52 (LOCF)
- Change from DB and LT baselines in the SDS total score at each scheduled assessment, Week 28 (LOCF) and Week 52 (LOCF)
- Change from DB and LT baselines in the HAM-A total score at each scheduled assessment, Week 28 (LOCF) and Week 52 (LOCF)

For the following variables, median survival time, its 95% confidence interval using the product-limit method will be calculated and Kaplan-Meier curve will be plotted for all patients and by treatment group in the prior study. The numbers and percentages of patients who experience a recurrence/relapse and all cause discontinuation will be summarized.

- Time to recurrence/relapse from the time when the symptoms associated with

- bipolar disorder have stabilized (see Section 3.4.1, Page 34)
- Time to all cause discontinuation from Day 1

Time to recurrence/relapse will also be analyzed separately for each type of episode of recurrence/relapse (major depressive, manic, hypomanic, or mixed episode) in the same way.

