3.6. CHANGES TO ANALYSIS FROM PROTOCOL

The only changes from the planned analysis stated in the protocol (V1.04, Dated 15MAR2016) are related to the subgroup analysis.

- Subgroups to consider: In section 9.5.3 of the protocol, the categories stated for the analysis by mood stabilizer are Lithium, VPA or None. Another category for "Both" (Lithium and VPA) is needed, according to the data collected.
- Efficacy subgroup analysis: Section 9.5.3 in the protocol states that "Subgroup analysis will be conducted for the change from DB and LT baselines in efficacy variables, such as the MADRS total score, the YMRS total score, the CGI-BP-S score (overall, depression, mania) and the HAM-A total score, as well as for the time to recurrence/relapse and time to all cause discontinuation, whenever appropriate.". Subgroup analysis have been included for the above variables with the only exception of the Hamilton Rating Scale for Anxiety (HAM-A).
- Safety subgroup analysis: In addition to the analysis stated in section 9.6.6 of the protocol for the safety variables, mood stabilizer and most recent or current episode subgroup analysis have also been conducted for the Columbia Suicide Severity Rating Scale (C-SSRS).

As per additional request, not initially contemplated in the protocol, a set of summaries containing disposition, demographic and baseline characteristics, exposure and compliance, efficacy and safety data will be added for Japanese subjects by most recent or current episode subgroup, splitting by presence or absence of a Major depressive episode. The details of these summaries are included in section 18 of the current document.

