16.1.5. SENSITIVITY ANALYSIS OF EFFICACY VARIABLE(S)

16.1.5.1. Time to Recurrence of a Major Depressive, Manic, Mixed or Hypomanic Episode

Time to recurrence of a DSM-IV-TR major depressive episode will be analyzed using a time-to-event analysis. KM results will be displayed for the 25%, 50% and 75% quartiles, including its 95% confidence interval using the product limit method. The KM figure will be produced to support the analysis.

Likewise, time to recurrence of any DSM-IV-TR manic, mixed or hypomanic episode will also be analyzed in the same way. For determining the above episode types, information will be used from the protocol-defined criteria for meeting a DSM-IV-TR event.

Time to recurrence of DSM-IV-TR major depressive episode, manic, mixed or hypomanic summaries will be presented for all subjects up to Week 28 and repeated for all Japanese subjects up to Week 52 separately.

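### SAP 16.1.2.1 times every type-specific recurrence from the first mood event of any type, so it cannot yield the analyses by episode type in SAP 16.1.5.1 and protocol 9.5.2

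*SAP*

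**What the plan says.** SAP 16.1.2.1 defines the variable: "Time to recurrence of a major depressive, manic, mixed or hypomanic episode is defined as ((date of first episode of any mood event", minus the clinical stability date, plus one. Its censoring sentence begins "When a subject completes the study without experiencing any mood event, the time to event may be censored at the time of study completion" and goes on to add discontinuation. No other SAP section derives this variable.

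SAP 16.1.5.1 describes the analysis. It plans a Kaplan-Meier analysis of DSM-IV-TR major depressive episodes, and then: "Likewise, time to recurrence of any DSM-IV-TR manic, mixed or hypomanic episode will also be analyzed in the same way". On classification it says: "For determining the above episode types, information will be used from the protocol-defined criteria for meeting a DSM-IV-TR event".

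Protocol 9.5.2 is the parent text: "Time to recurrence/relapse will also be analyzed separately for each type of episode of recurrence/relapse", with the four types listed. Protocol 6.2.7 has the date, the criterion met and the type of a recurrence or relapse recorded in the eCRF, and the number of episodes in the treatment phase counted by type.

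For the main any-mood-event endpoint, SAP 16.1.1.6 lists five relapse criteria, of which only the first is meeting DSM-IV-TR criteria for an episode. Its censoring rule is firm: "Time to recurrence will be censored at the time of study completion or early termination", for subjects without any recurrence.

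**The concern.** The derivation and the analysis describe different events. The derivation stops the clock at the first mood event, whatever its type. The analysis wants the first episode of a named type. A programmer working from 16.1.2.1 would produce one curve under several titles.

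A programmer who works from 16.1.5.1 instead gets type-specific events but meets a second problem. Two groups have had a mood event that is not the event being analysed: subjects whose first relapse is of another type, and subjects whose first relapse meets only criteria 2 to 5 (treatment intervention, psychiatric hospitalization, rating scores, discontinuation for a mood episode). The censoring sentence covers only subjects with no mood event at all, so neither group has a rule.

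At stake is whether the reported percentages and quartiles by episode type mean what their titles say, and whether two programmers would get the same numbers.

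**Working it through.** The plan states no relapse rate or event count for this endpoint, so there is no figure of its own to reproduce. The check compares the texts and then uses assumed data.

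**Texts side by side**

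- Event in 16.1.2.1: first mood event of any type. Event in 16.1.5.1: DSM-IV-TR episode of a named type. Both cannot hold, because a first manic episode is an event in the depressive analysis under one and not under the other.
- Reading 16.1.2.1 as a composite of all DSM-IV-TR episodes does not reconcile them, since 16.1.5.1 plans no such composite.
- The censoring sentences in 16.1.1.6 and 16.1.2.1 apply only to subjects with no mood event, so neither fills the gap.
- Three rules remain open for an earlier different relapse: censor at that relapse, treat it as a competing event, or keep the subject at risk until completion or discontinuation. The third is a real option. Protocol 4.4.1 requires treatment to stop for pregnancy and for adverse events or lack of efficacy leading to hospitalization, not for every relapse, and protocol 6.2.7 foresees repeated episodes.

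**Illustration (assumed data)**

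Ten stable subjects have five first relapses, in the order manic-type, depressive, manic-type, depressive, manic-type. The other five are followed to the end without relapse. Manic, mixed and hypomanic are grouped as manic-type for illustration only. For the kept-at-risk rows, all ten are assumed to be followed to the end, so Kaplan-Meier reduces to a proportion.

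| Rule for a first relapse of another type | Depressive | Manic-type |
|---|---|---|
| Literal 16.1.2.1 | 5/10 = 50.0% | 5/10 = 50.0% |
| Censored at that relapse | 1 − (8/9)(6/7) = 23.8% | 1 − (9/10)(7/8)(5/6) = 34.4% |
| Competing event (cumulative incidence) | 2/10 = 20.0% | 3/10 = 30.0% |
| Kept at risk, no later episode of the named type | 2/10 = 20.0% | 3/10 = 30.0% |
| Kept at risk, one later episode of the named type | 3/10 = 30.0% | 4/10 = 40.0% |
| Kept at risk, every other-type relapser later has one | (2+3)/10 = 50.0% | (3+2)/10 = 50.0% |

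Changing the order of the five relapses, with one to four of them depressive, puts the gap between censoring and cumulative incidence anywhere from 0.0 to 8.6 points. The maximum is 1 − (6/7)(5/6) = 28.6% against 20.0%.

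**Relapses meeting only criteria 2 to 5.** If one of the two depressive relapses is of this kind and is not counted, cumulative incidence falls from 20.0% to 1/10 = 10.0%. With censoring, 23.8% falls to 1 − 6/7 = 14.3% if it is the second relapse, or to 1 − 8/9 = 11.1% if it is the fourth.

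**Constant hazards.** Let r be the probability of any relapse and s the share of relapses of the named type. Censoring gives 1 − (1 − r)^s and cumulative incidence gives r × s.

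- r = 0.10, s = 0.3: 3.1% against 3.0%.
- r = 0.50, s = 0.5: 29.3% against 25.0%.
- r = 0.60, s = 0.5: 36.8% against 30.0%.

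For r from 10% to 50% and s from 30% to 70%, the gap is 0.1 to 4.3 points. These gaps compare two of the three open rules. The kept-at-risk rule can move the result further, as the table shows.

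**The case against.** The strongest reply is that this is loose drafting that would correct itself. Identical curves defeat the stated purpose of 16.1.5.1, a programmer would probably notice, and the output templates mentioned in SAP section 8 may settle it. The variable is labelled a sensitivity variable, the study has no hypotheses, and the main endpoint has its own derivation. That fairly limits the importance. It does not make the sentence in 16.1.2.1 right, and the templates are not among the documents. Nor does it supply a rule for the two uncovered groups.

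The permissive verb in the censoring sentence is a small matter, since a subject without an event can hardly be handled otherwise in a Kaplan-Meier analysis. It is worth tidying and no more.

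A reader might also infer three stronger things that the documents do not support:

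- **That the SAP silently narrowed the protocol.** SAP 3.6 states "The only changes from the planned analysis stated in the protocol (V1.04, Dated 15MAR2016) are related to the subgroup analysis", and 16.1.5.1 takes type from the DSM-IV-TR criterion. But protocol 9.5.2 names the same four episode types as the DSM-IV-TR relapse criterion, so it may already mean DSM-IV-TR episodes. The broader reading is possible, because protocol 6.2.7 records type along with whichever criterion was met. The text does not decide between them.
- **That manic, mixed and hypomanic episodes are pooled.** The closing sentence of 16.1.5.1, "Time to recurrence of DSM-IV-TR major depressive episode, manic, mixed or hypomanic summaries will be presented for all subjects up to Week 28", fits separate summaries equally well.
- **That cumulative incidence must replace Kaplan-Meier.** Both documents specify the product-limit method. With a stated rule and a matching label, that method is acceptable here. A manic relapse does not preclude a later depressive episode, so treating it as a competing event is itself a choice of quantity.

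**Conclusion.** The point holds as a minor one. The event definition in SAP 16.1.2.1 is wrong for the analyses it serves, and no other section repairs it. Once 16.1.5.1 is taken to define the event, subjects with an earlier different relapse have no stated handling under any of three reasonable rules.

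The numbers rest entirely on assumed data and show only that the choice can matter by several points or more; no bound can be given. The effect is limited to descriptive curves by episode type. A reader might infer that the main time-to-relapse result or some test is compromised. It is not: 16.1.1.6 defines the any-mood-event endpoint and its censoring separately, and the study tests no hypothesis.

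**What to change.** In SAP 16.1.2.1:

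1. Define the event for each analysis as the first post-stability DSM-IV-TR episode of the named type.
2. State firmly, not permissively, that subjects without such an episode will be censored at completion or discontinuation, subject to rule 3.
3. State one rule for an earlier relapse of another type or one meeting only criteria 2 to 5, and label the curve to match.
   - If dates of later episodes are captured, keep the subject at risk. This also retains a subject who meets a score or treatment criterion shortly before fulfilling DSM-IV-TR criteria for the same episode.
   - If they are not, redefine the event as a first relapse that is itself a DSM-IV-TR episode of the named type and censor at the other relapse. Footnote that the curve is cause-specific and that the censoring may be informative.
4. Cumulative incidence may be added as a supportive display beside the planned product-limit curves.

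If protocol 9.5.2 was meant to cover relapses of each type under any criterion, list the DSM-IV-TR restriction, and any pooling of types, in SAP 3.6.

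The cost is SAP wording and derivation code. The censoring variant needs only the relapse date, criterion and type recorded under protocol 6.2.7. The kept-at-risk variant also needs dates of later episodes. The protocol does not show that these are collected, so the sponsor should check this before choosing.

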16.1.3. MISSING DATA METHODS FOR EFFICACY VARIABLE(S)

In the event that any of the component elements of a total score are missing, the total score will be set to missing.

Missing data will be accounted for using a LOCF method to impute the Week 28 (LOCF) endpoint and the Week 52 (LOCF) endpoint values only. For calculation details, please see section 6.3.

Document: K:\DSP\SM-13496\RVA97109\Biostatistics\Documentation\SAP
Author: [REDACTED] Version Number: 1.0
Version Date: 20MAR2018

Template No: CS_TP_BS016 – Revision 3 Reference: CS_WI_BS005
Effective Date: 01May2012

Copyright © 2012 [REDACTED] All rights reserved.
The contents of this document are confidential and proprietary to [REDACTED]. Unauthorized use, disclosure or reproduction is strictly prohibited.

16.1.4. ANALYSIS OF EFFICACY VARIABLE(S)

16.1.4.1. Analysis of MADRS, YMRS, CGI-BP-S, SDS and HAM-A

Observed and change from DB baseline and LT baseline to each post-baseline visit including Week 28 (LOCF) endpoint and Week 52 (LOCF) endpoint for subject within Japan, will be summarized for the safety population by treatment group for the following scores:

- MADRS total score
- YMRS total score
- CGI-BP-S overall score
- CGI-BP-S depression score
- CGI-BP-S mania score
- SDS total score and subscale scores of work/school, social life or leisure activities, and home life or family responsibilities, and days lost and days underproductive
- HAM-A total score

MADRS total score, YMRS total score and CGI-BP-S overall score summaries will be presented for all subjects up to Week 28 overall, by country (excluding Japan), Sex, Age and Mood Stabilizer subgroups separately, and will be repeated for all Japanese subjects up to Week 52 overall, by Sex, Age, Mood Stabilizer, Most Recent or Current Episode, Bipolar I Subtype and Psychotic Features subgroups separately as well.

CGI-BP-S depression and mania score summaries will be presented for all subjects up to Week 28 overall and by country (excluding Japan) separately, and will be repeated for all Japanese subjects up to Week 52 overall, by Sex, Age, Mood Stabilizer, Most Recent or Current Episode separately as well.

SDS total score and subscale scores and HAM-A total score summaries will be presented for all subjects up to Week 28 and repeated for all Japanese subjects up to Week 52.

16.1.4.2. Time to recurrence/relapse of any mood event from clinical stability of bipolar I disorder

Time to recurrence/relapse of any mood event from clinical stability of bipolar I disorder will be analyzed using a time-to-event analysis. Kaplan-Meier (KM) results will be displayed for the 25%, 50% and 75% quartiles, including its 95% confidence interval using the product limit method. The KM figure will be produced to support the analysis. The time to recurrence/relapse of any mood event from clinical stability of bipolar I disorder will be presented for all subjects up to Week 28 overall, by country, Sex, Age and Mood Stabilizer separately, and will be repeated for all Japanese subjects up to Week 52 overall, by Sex, Age, Mood Stabilizer, Most Recent or Current Episode, Bipolar I Subtype and Psychotic Features separately as well.

Time to recurrence/relapse of any mood event from clinical stability of bipolar I disorder for subjects with more than 28 Weeks of treatment duration after clinical stability will also be analyzed using a time-to-event analysis and will be presented for all Japanese subjects up to Week 52.

The frequency and percentages of subjects with clinical stability as well as subject who experience a recurrence/relapse of any mood event from clinical stability will be summarized as well as the duration of stabilization which will be summarized descriptively. Summaries will be based on the safety population, by

Document:	K:\DSP\SM-13496\RVA97109\Biostatistics\Documentation\SAP		
Author:	[REDACTED]	Version Number:	1.0
		Version Date:	20MAR2018

Template No: CS_TP_BS016 – Revision 3
Effective Date: 01May2012

Reference: CS_WI_BS005

Copyright © 2012 [REDACTED] All rights reserved. [REDACTED]
The contents of this document are confidential and proprietary to [REDACTED]. Unauthorized use, disclosure or reproduction is strictly prohibited.

treatment group for all subjects up to Week 28 overall and by country separately, and will be repeated for all Japanese subjects up to Week 52 separately as well.

